#### 3.9.2.4 Study Acknowledgment

All manuscripts derived from data collected by CKiD must include the following acknowledgment:

Data in this manuscript were collected by the Chronic Kidney Disease in children prospective cohort study (CKiD) with clinical coordinating centers (Principal Investigators) at Children's Mercy Hospital and the University of Missouri – Kansas City ([name]) and Children's Hospital of Philadelphia ([name], Ph.D.), Central Biochemistry Laboratory ([name]) at the University of Rochester Medical Center, and data coordinating center at the Johns Hopkins Bloomberg School of Public Health ([name].) (U01-DK-66143, U01-DK-66174, U01-DK-82194, U01-DK-66116). The CKiD is funded by the National Institute of Diabetes and Digestive and Kidney Diseases, with additional funding from the National Institute of Child Health and Human Development, and the National Heart, Lung, and Blood Institute. The CKID website is located at https://statepi.jhsph.edu/ckid/.

#### 4. STUDY METHODS

#### 4.1 Study Design

The design of the CKiD study is a prospective, observational cohort of children with chronic kidney disease. Exposures will be measured at baseline and scheduled annual follow-up visits will permit the subsequent updating of the exposures in cohort participants. Outcomes will also be assessed at the annual visits and they include: measures of kidney function; neurocognitive function; markers of risk factors for cardiovascular disease; growth and other co-morbid conditions. The study will use the power of the cohort design with regularly scheduled visits at which markers of disease progression will be measured under standardized procedures. Levels and longitudinal changes in markers will constitute the primary outcomes. The study will collect data on clinical events with primary interest in ESRD and death. Such events will provide time-to-event data to determine heterogeneity of times to ESRD in children with mild to moderate chronic kidney disease.

#### 4.2 Study Population

The CKiD study population will include three cohorts. Cohort 1 includes approximately 600 racially and ethnically diverse children, age 1-16 years old with mildly to moderately impaired kidney function, defined by an estimated GFR between 30 and 90 ml/min|1.73m^2 by the Schwartz formula (sGFR). Cohort 2 includes approximately 300 children with more mildly impaired kidney function, defined as an estimated GFR between 45 and 90 by the updated Schwartz formula (eGFR). In addition, Cohort 2 was compromised of approximately 150 children with glomerular disease and approximately 150 children with non-glomerular causes of disease. Cohort 3 will include 190 children with non-glomerular diagnosis and duration of kidney disease less than 5 years but age at enrollment could range from 6 months to 16 years old.

Table 4.2 describes the number of children in each stratum of age and estimated GFR that were recruited in Cohort 1. The high frequency of children with an estimated GFR between 40 and 59 ml/min|1.73m^2 (206) will empower the study to describe the

heterogeneity of progression in children with renal insufficiency. Among the 276 children with an estimated GFR between 60 to 90. there will be a subset of nonprogressors who will play the role of "controls" and can be expected to be followed for a longer period of time; in contrast, the highest frequency of fast progressors will be expected among those with GFR between 30 39 to ml/min|1.73m^2 at baseline. The distribution by age is based on observed rates in the North American Pediatric Cooperative

sGFR	14	5-10	11-16	Total
60-90	49	93	134	276
40-59	32	83	91	206
30-39	18	37	49	104
Total	99	213	274	586

asGFR = (k x body length / serum creatinine)

```
where k=0.45, 0.55, 0.70 according to age-gender categories
```

Study [NAPRTCS 2002] CRI registry. In the NAPRTCS registry, 18% of the children are age 1 to 5, 52% are age 6 to 12, and 30% are age 11 to 16. In comparison, the age of the cohort will be stratified into the following three age groups: 1 to 4; 5 to 10; and 11 to 16 years. Therefore, the percentages have been adjusted to recruit a higher number of children in the oldest age group, 16%, 36% and 47%, respectively.

In Cohorts 1 and 2, children less than one year old were not enrolled; however, in cohort 3 we will focus on enrolling children close to their onset of kidney disease. Therefore, we will enroll children as young as 6 months old. The upper limit of 16 years was chosen to optimize follow-up for all subjects to be followed for at least four years, since the subjects would likely remain under the care of the pediatric nephrology centers enrolling patients.

Based on estimates from both CCCs, in Cohort 1 we expected 56% Caucasian, 24% African-American, 15% Hispanic, and 5% Asian, Pacific Islander, American Indian, or other, and we placed an upper limit of 65% for the percent of the cohort that would be Caucasian. In Cohort 1, 37% of children with glomerular disease were African-American. Since the study expected to enroll a higher proportion of children with glomerular disease in Cohort 2, it was also expected that there would be more African-American children enrolled resulting in more generalizable study population. However, there were similar percentages of African-Americans enrolled in both cohort, 23% and 20% respectively. In Cohort 3, we expect to enroll a similar percentage of African-Americans and we will place an upper limit of 65% for Caucasian enrollment. Also, based on estimates from the east coast CCC, we expect that overall 40% of the combined cohort will be female.

#### 4.2.1 Inclusion Criteria

Determining eligibility is a multi-step process involving the review of medical information, participant interview, and conference with the participant's health care provider and the PI. Information collected on the Eligibility Form represents the first step in determining a participant's eligibility based on available information.

Eligibility for Cohort 1 was determined by obtaining two estimated GFR measurements, with a value between 30 to 90 ml/min| $1.73m^2$ . The first measurement must be within the past six months and the second measurement within the past 18 months. Specifically, the GFR will be estimated using the Schwartz formula (GFR = kL/SCr), where k is 0.45 for males and females 12 months to 18 months; 0.55 for males between 19 months and 13 years (before 13th birthday) and females 19 months and older ; and 0.7 for males after 13th birthday. Tables 5.2.1a, 5.2.1b and 5.2.1c in the study recruitment section provide the interval of serum creatinine that would enable a child to participate according to his/her height. For example, males 13 years old and older whose height is 122 cm will be eligible to be included as participants if the SCr is between 1.1 (corresponding to a GFR of 90) and 2.8 mg/dl (corresponding to a GFR of 30).

Eligibility for Cohort 2 was determined by obtaining two estimated GFR measurements, with a value between 45 to 90 ml/min|1.73m^2. Similarly to Cohort 1, the first measurement must be within the past six months and the second measurement within the past 18 months. However, the GFR was estimated using the updated Schwartz

formula (eGFR = 41.3 [height /  $S_{Cr}$ ]) for height measured in meters. If height is measured in centimeters (cm), then the formula is eGFR = 0.413 [height /  $S_{Cr}$ ]. For Cohort 2, recruitment efforts were focused on enrolling an equal distribution of children with glomerular and non-glomerular disease.

Eligibility for Cohort 3 will be determined by having a Non-Glomerular diagnosis of CKD whose duration is less than 5 years at date of enrollment and age between 6 months to 16 years old. In order to assure that CKD is present, for specific non-glomerular diagnoses, we will require two or more of the following: 1) urine protein to creatinine ratio greater than 0.5 for children less than 2 years old, or urine protein to creatinine ratio greater than 0.2 for children 2 years of age and older; 2) hematuria (for at least 3 months): 3) evidence of renal tubular disorders; 4) abnormalities detected by kidney biopsy or imaging (bilateral disease or solitary kidney disease); 5) a serum creatinine measurement greater than 0.4mg/dL for children less than 2 years old, or, for children 2 years of age and older, an estimated Glomerular Filtration Rate (eGFR) less than 90 ml/min|1.73m^2 based on the updated Schwartz formula; or 6) hypertension defined by documented note in medical record, current treatment of hypertension, or blood pressure > 95th percentile on at least two occasions. Additionally, these conditions must have occurred after the initial 6 months of life (with the exception of abnormalities detected by kidney biopsy or imaging) and must not be secondary to a current or resolving episode of acute kidney injury. Since description of course to renal replacement therapy is of primary interest, children who are expected to receive renal replacement therapy within 6 months of date of enrollment will not be recruited. Eligible children must be willing to complete baseline and follow-up testing, and all procedures at scheduled annual visits for the duration of the study. Spanish-speaking children and children who are blind and/or deaf who meet the inclusion criteria will be eligible for study participation if they are able to complete either the neurocognitive or behavioral assessments of the neuropsychological component and all other study procedures. Since retention in a cohort study is of central importance, numerous efforts will be employed to include in the cohort children with the highest likelihood of participation in the study for the long term. Also, children can be included in the study only if they and their parents/legal guardians are willing and able to provide informed consent and assent.

In summary, the following conditions comprise the inclusion criteria:

- Age between 1 and 16 years (before 17th birthday) for Cohorts 1 and 2; age between 6 months and 16 years (before 17th birthday) for Cohort 3
- Estimated (based on Scr) Schwartz GFR between 30 and 90 ml/min|1.73m^2 for Cohort 1 OR an estimated GFR between 45 and 90 ml/min|1.73m^2 based on the updated Schwartz formula for Cohort 2
- Willingness and ability to provide informed consent and assent
- For Cohort 2, an equal distribution of children with glomerular and nonglomerular causes of disease were enrolled (i.e., 150 within each) and the study placed an upper limit of 60% for the percent of enrolled with nonglomerular disease.

• For Cohort 3, 190 children with non-glomerular diagnosis and duration of kidney disease less than 5 years will be enrolled.

Patients with the non-glomerular diagnoses listed below that meet the initial criteria (i.e., duration of kidney disease less than 5 years, and age between 6 months and 16 years old) are eligible and do not have to meet additional criteria:

- Branchio-oto-Renal Disease/Syndrome
- Cystinosis
- Medullary cystic disease/ juvenile nephronophthisis
- Methylmalonic Acidemia
- Oxalosis
- Polycystic kidney disease (Autosomal recessive)

However, all other patients with non-glomerular diagnoses will require at least two of the following conditions. All conditions except for abnormal imaging/biopsy must have occurred after the initial 6 months of life and must not be secondary to a current or resolving episode of Acute Kidney Injury (AKI):

- o significant proteinuria,
  - Age < 2 years old: urine protein to creatinine ratio > 0.5
  - Age ≥ 2 years old: urine protein to creatinine ratio > 0.2
- o hematuria (for at least 3 months),
- evidence of renal tubular disorders,
- o abnormalities detected by kidney biopsy or imaging
- o abnormal kidney function
  - Age < 2 years old: serum creatinine > 0.4 mg/dL
  - Age  $\geq$  2 years old: eGFR < 90 ml/min|1.73m^2

(eGFR=41.3 x height[meter]/creatinine[mg/dL])

- Hypertension defined by one of the following:
  - Documented hypertension noted in the medical record by the physician
  - Current treatment of hypertension
  - Blood pressure > 95th percentile for age and gender on at least two occasions

#### 4.2.2 Exclusion Criteria

Among the children who fulfill the inclusion criteria, certain medical conditions and/or the inability to assess exposures of interest will deem them ineligible. Specifically, the following conditions comprise the exclusion criteria:

- Renal, other solid organ, bone marrow or stem cell transplantation
- Dialysis treatment within the past three months
- Cancer diagnosis or HIV diagnosis/treatment within last twelve months
- Current pregnancy or pregnancy within past twelve months
- Inability to complete major data collection procedures
- Current enrollment in a randomized clinical trial in which the specific treatment is unknown
- Not fluent in English or Spanish
- Plans to move out of area of any participating CKiD site (Families can be transferred to another CKiD site if they move)
- History of structural heart disease
- Genetic syndromes involving the central nervous system (e.g., Downs syndrome)
- History of severe to profound mental retardation (i.e., IQ<40, significant impairment in adaptive function and/or inability to independently execute selfcare skills)
- For cohort 3, children who are expected to receive renal replacement therapy within 6 months of date of enrollment will not be recruited.

#### 4.2.3 Recruitment of Additional African-American Children

After reaching the original recruitment goal of 540 children, cohort 1 was comprised of a 15% African-American population. So the study continued to recruit an additional 60 African-American children, which resulted in a racial demographic of 23%. To accomplish the goal of recruiting more African-American children, the study targeted recruitment at a selected number of sites located in geographical areas with high percentages of minorities (i.e., Washington, DC, Brooklyn, NY, Chicago, IL) and encouraged sites to recruit African-Americans during Steering Committee and coordinator conference calls. In Cohort 2, targeted recruitment of additional African-Americans was not done. The study will monitor the recruitment of African-American and if necessary targeted recruitment at selected sites will be completed to ensure the study recruits a generalizable population of African-Americans.

#### 5. RECRUITMENT/FOLLOW-UP

#### 5.1 Overview of Recruitment

In Cohort 1, each Clinical Coordinating Center was committed to recruiting 300 participants into the CKiD Study. In Cohort 2, each was committed to recruiting 140. In Cohort 3, each CCC is committed to recruiting 95 participants. Recruitment sources and strategies will vary from site to site, but will most likely include computerized database searches, manual searches of medical records, referrals from health care providers, and patient panels of CKiD investigators. Investigators are encouraged to present the CKiD study to their colleagues as well as to discuss it with other health care providers, particularly pediatricians and nephrologists in their area. A patient brochure and study poster will describe the basic study objectives and information on how to join the study and can be used to recruit participants and remind clinical staff of the study. Further recruitment and referral information will be presented through advertisements in the National Kidney Foundation Newsletter "Family Focus", through posters and presentations at national scientific meetings of Pediatric Nephrology, and/or the website of the Kidney and Urology Foundation of America.

#### 5.2 Recruitment Process

In Cohort 1, each clinical site identified potentially eligible participants, age 1-16 years with reduced kidney function based on an estimated GFR of 30-90 ml/min/1.73m^2. In Cohort 2, clinical sites identified eligible participants with an estimated GFR of 45-90 based on the updated Schwartz formula. In Cohort 3, clinical sites will identify eligible participants with duration of CKD less than 5 years and serum creatinine greater or equal to 0.5 mg/dl. Eligible participants will be identified via recruitment sources and strategies available at their particular site. These include, but are not limited to, automated laboratory database searches for eligible patients age 6 months to 16 years with reduced kidney function, referrals from physicians or specialty centers of potential participants, self-referral from potential participants who may respond to the study brochure or poster or hear about the study from relatives or friends. In contrast to the recruitment efforts of Cohort 1 where 78% of the cohort had non-glomerular disease, the recruitment process of Cohort 2 focused on enrolling an equal distribution of children with glomerular and non-glomerular disease. Specifically, it was expected that 50% of the children in Cohort 2 would have glomerular disease and the study placed an upper limit of 60% for the percent of enrolled with non-glomerular disease. When recruitment approached the upper limit, sites were notified that recruitment efforts should be focused on enrolling only children with glomerular disease. In Cohort 3, all children will have non-glomerular disease.

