#### 5.2.1 Identifying potential participants

In the recruitment efforts for Cohort 1, Tables 5.2.1a, 5.2.1b and 5.2.1c showed the ranges of  $S_{Cr}$  that correspond to a GFR between 30 and 90 ml/min|1.73m^2 for children of different genders and heights. The lower serum creatinine limit of the range corresponds to an estimated GFR of 90 ml/min|1.73m^2 and the higher limit corresponds to an estimated GFR of 30 ml/min|1.73m^2.

In Cohort 2, Table 5.2.1d showed the ranges of  $S_{Cr}$  that correspond to an estimated GFR between 45 and 90 based on the updated Schwartz bedside formula. Similarly to Cohort 1, the lower serum creatinine limit of the range corresponds to an estimated GFR of 90 ml/min|1.73m^2 and the higher limit corresponds to an estimated GFR of 45 ml/min|1.73m^2 and two estimated GFR measurements will be required for study enrollment. The first measurement must be within the past six months and the second measurement within the past 18 months.

Eligibility for Cohort 3 will be determined by having a non-glomerular diagnosis of CKD whose duration is less than 5 years at date of enrollment and age between 6 months to 16 years old. In order to assure that CKD is present, for specific non-glomerular diagnoses, at least two more conditions must be met as outlined in the inclusion criteria under section 4.2.1. One of the additional criteria is the presence of abnormal kidney function. Unlike Cohort 1 and 2, the presence of abnormal kidney function is an optional eligibility criteria for Cohort 3. If abnormal kidney function is not present, a child is still eligible if they meet at least two of the other conditions. For Cohort 3, abnormal kidney function is defined as having a serum creatinine measurement greater than 0.4mg/dL for children less than 2 years old, or, for children 2 years of age and older, an estimated GFR less than 90 ml/min|1.73m^2 based on the updated Schwartz formula. Table 5.2.1e shows the ranges of SCr that correspond to an estimated GFR  $\leq$  90 ml/min|1.73m^2 for children for different heights who are 2 years old and older.

Height		SCr		Hei	ght	SCr		Height		SCr				
(cm)	(in)	Low	-	High	(cm)	(in)	Low	-	High	(cm)	(in)	Low	-	High
45	17.7	0.23	-	0.67	57	22.4	0.29	-	0.85	69	27.2	0.35	-	1.03
46	18.1	0.23	-	0.69	58	22.8	0.29	-	0.87	70	27.6	0.35	-	1.05
47	18.5	0.24	-	0.70	59	23.2	0.30	-	0.99	71	28.0	0.36	-	1.06

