#### Table 5.2.1e, Eligible SCr ranges\* by height based for Cohort 3 children 2 years old or older

\*Serum Creatinine Range correspond to an eGFR  $\leq$  90 ml/min|1.73m^2 for children of different heights who are  $\geq$  2 years old

**EXAMPLE:** 3 year old whose height is 84 cm will be eligible if the  $S_{Cr}$  is  $\ge$  0.39 [ $S_{Cr} = 0.41$  (eligible);  $S_{Cr} = 0.22$  (ineligible)]

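### Section 5.2 gives sites a flat serum creatinine floor of 0.5 mg/dl for finding Cohort 3 children; this contradicts the Cohort 3 criteria in sections 4.2.1 and 5.2.1 and could miss eligible children below the floor

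*Protocol*

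**What the plan says.** Section 5.2 gives one sentence per cohort on whom the sites identify. For Cohorts 1 and 2 the sentence carries the actual eligibility range (eGFR 30 to 90 and 45 to 90). For Cohort 3 it reads "clinical sites will identify eligible participants with duration of CKD less than 5 years and serum creatinine greater or equal to 0.5 mg/dl", with no qualifier for age, height or diagnosis.

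The other Cohort 3 text differs:

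- **Section 4.2.1.** Children with one of six listed non-glomerular diagnoses who meet the age and duration limits "are eligible and do not have to meet additional criteria". All others need at least two of six conditions. Abnormal kidney function is one of the six, defined as "Age < 2 years old: serum creatinine > 0.4 mg/dL" or, from age 2, eGFR below 90 with eGFR = 41.3 × height (m) / creatinine.
- **Section 5.2.1.** It states that "the presence of abnormal kidney function is an optional eligibility criteria for Cohort 3". It adds: "If abnormal kidney function is not present, a child is still eligible if they meet at least two of the other conditions".
- **Table 5.2.1e** (age 2 and over). Cut-offs run from 0.23 mg/dL at 50 cm to 0.87 at 189 cm. In its example a "3 year old whose height is 84 cm will be eligible if the" creatinine is 0.39 or more; 0.41 is labelled eligible and 0.22 ineligible.

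A general creatinine floor of 0.5 mg/dl appears in neither the inclusion nor the exclusion list.

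**The concern.** The protocol gives sites two incompatible descriptions of who belongs in Cohort 3. One requires a minimum creatinine. The other does not require reduced function at all and, where function is used, sets lower cut-offs for small children.

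Creatinine rises with body size at a given eGFR, so a flat floor falls hardest on the smallest children. Those children matter here. Section 4.2 lowers the minimum age to 6 months so as to enrol close to onset, duration must be under 5 years, and section 8.1.2 notes that non-glomerular disease is most often diagnosed at birth. Section 9.1 sizes the cohort at 190 to estimate the rates of conditions such as acidosis. If entry depends on creatinine, those rates describe a group with more reduced function than section 4.2.1 defines. Sites that follow different sections would also draw from different populations.

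**Working it through.** **Inputs.** Floor: creatinine 0.5 mg/dl (section 5.2). Functional cut-offs: creatinine above 0.4 under age 2, eGFR below 90 from age 2, with eGFR = 41.3 × height (m) / creatinine (section 4.2.1). Printed cut-offs and example: Table 5.2.1e. Precision formula: section 9.1.

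**1. Reproduce the plan's table.** Creatinine at eGFR 90 = 0.413 × height (cm) / 90.

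- 84 cm: 0.413 × 84 / 90 = 0.3855 (printed 0.39)
- 107 cm: 0.4910 (printed 0.49)
- 108 cm: 0.4956 (printed 0.50)
- 150 cm: 0.6883 (printed 0.69)

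Thirteen heights between 50 and 189 cm were checked and all agree.

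**2. Where the floor and the eGFR criterion meet.** 90 × 0.5 / 0.413 = 108.96 cm. The printed cut-off is below 0.50 at every height from 50 to 107 cm.

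**3. What the floor means from age 2.** eGFR at creatinine 0.5 = 41.3 × height (m) / 0.5.

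| Height (cm) | Table 5.2.1e cut-off (mg/dL) | eGFR at 0.5 mg/dl |
|---|---|---|
| 84 | 0.39 | 69.4 |
| 90 | 0.41 | 74.3 |
| 100 | 0.46 | 82.6 |
| 107 | 0.49 | 88.4 |
| 109 | 0.50 | 90.0 |
| 120 | 0.55 | 99.1 |
| 150 | 0.69 | 123.9 |

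Below about 108 cm the floor acts as an eGFR ceiling under 90. From about 109 cm it loses no child with eGFR below 90.

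**4. The protocol's own example.** 41.3 × 0.84 / 0.41 = 84.6, which is below 90, so the condition is met; but 0.41 is below 0.5. At 84 cm, creatinine from 0.39 to 0.49 (eGFR 89.0 down to 70.8) meets the functional condition and fails the floor.

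**5. Under age 2.** The criterion is creatinine, not eGFR. The gap is creatinine above 0.4 and below 0.5, whatever the height.

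**6. Children who need no functional condition.** A child with a listed diagnosis, or with two other conditions, is eligible at any creatinine. The floor drops every such child below 0.5, at any height.

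**7. Bearing on the 190.** n = 1.96² p(1 − p) / (p/2)². With p = 0.075 this is 3.8416 × 0.069375 / 0.00140625 = 189.5, which matches the stated 190. A floor leaves n unchanged but changes the population whose p is estimated, and a larger n would not correct that.

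**The case against.** The best defence is that section 5.2 describes case-finding and is not the rule for admission. Its sources are open-ended and include referral and self-referral. The next subsection restates Cohort 3 eligibility in full, section 4.2.1 makes eligibility a multi-step review, and section 11.3.3 requires the inclusion and exclusion criteria to be met. A child who reaches that review would not be turned away for a creatinine of 0.45. This stands: the formal criteria govern. But they cannot recover a child who was never identified. The sentence speaks of eligible participants, sits beside two sentences that give true eligibility ranges, and is followed by laboratory database searches for patients with reduced function, into which a single number is easily coded.

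It also stands that under age 2 the functional gap is narrow. A laboratory that reports to one decimal would see no difference between above 0.4 and at least 0.5. Table 5.2.1e works to two decimals.

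Two stronger readings are tempting, and the protocol supports neither:

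- A reader might infer that the floor screens out early-disease children in general. Sections 4.2 and 9.1 define early by duration and closeness to onset, not by creatinine. Entry runs to age 16, and taller children with recent onset pass the floor even with eGFR above 90. Nor does restriction on baseline function in itself bias slopes; Cohorts 1 and 2 were defined that way.
- A reader might infer that section 5.2 is the only text out of line. Table 5.2.1e labels its 84 cm child with creatinine 0.22 ineligible without qualification, although that child could qualify by a listed diagnosis or by two other conditions. The table also uses eGFR at or below 90, where sections 4.2.1 and 5.2.1 use below 90.

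**Conclusion.** The contradiction is real and can be checked within the protocol alone. The Cohort 3 sentence in section 5.2 states a threshold that the formal criteria do not contain and that the protocol's own example fails. Its reach is limited to children with creatinine below 0.5, in the three groups set out in steps 3 to 6 of the working. If the floor is used to find cases, Cohort 3 condition rates shift toward more reduced function.

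Two things remain unknown. The protocol gives no creatinine distribution for Cohort 3, so neither the number of children lost nor the size of the shift can be computed. Nothing shows that any site has applied the floor. The eGFR figures assume the updated Schwartz formula as section 4.2.1 states it.

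**What to change.** - **Section 5.2:** replace the creatinine clause for Cohort 3 with a reference to the Cohort 3 criteria in section 4.2.1, and say that a laboratory search alone is not the Cohort 3 screen. If the investigators did intend a floor, sections 4.2.1 and 5.2.1 and Table 5.2.1e would have to be reconciled to it instead.
- **Table 5.2.1e:** state that the ranges define only the optional abnormal-function condition, correct the unqualified label on the 0.22 example, and use the same inequality at eGFR 90 as section 4.2.1.
- **Sites:** notify them, and ask each whether it has applied the 0.5 floor since Cohort 3 recruitment began in late September 2016 (Appendix D). Record the answers so that any selection can be described with the results.

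The cost is a few sentences in an amendment, one memo and one question per site. The sample size and the analyses do not change.
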